8.2. Study population

The study cohort will be defined as patients diagnosed with VTE between 1 Mar 2013 and 30 Jun 2019. The cohort entry will be defined as the date of incident VTE diagnosis. The index date will be defined as the date of first prescription for anticoagulants within 30 days after the index VTE event. The length of the exclusion assessment window will vary depending on the condition, from 12-months at minimum to anytime prior to index date. The following patients will be excluded: A record of VTE diagnosis within the 12-month period prior to the index VTE encounter, diagnosed with atrial fibrillation, atrial flutter, mechanical heart valve replacement or mitral stenosis anytime prior to index date, had a record of Inferior Vena Cava filter anytime prior to index date, received anticoagulatory therapy within the 12-month period prior to index VTE encounter to restrict to new users of anticoagulatory therapy, prescribed two different anticoagulants on the same index date to prevent exposure misclassification, had a record of pregnancy within the 9-month period prior to index date, and for the Phase II of the study only, had a record of active cancer within six months period prior to index date.

Baseline sociodemographic characteristics (e.g., age, sex) will be assessed on the index date, whereas clinical characteristics (comorbidities, previous use of medications, Charlson comorbidity index [CCI], HAS-BLED scores, initial presentation of VTE, number of outpatient visits) will be assessed in the 6-month period prior to the index date except when otherwise specified in section 8.4 *Variables* (Figure 2).

Within this study cohort, we will describe the treatment patterns of anticoagulants prescribed for VTE treatment throughout the period of follow-up, defined as the period from the index date to the end of the study period. Moreover, if feasible, we will also examine the risk of major bleeding overall and by site, associated with each NOAC use, as compared with warfarin.

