- The risk of major bleeding according to the treatment of interest will be investigated in time-to-event analyses using standard Kaplan-Meier methods.

- Cox proportional hazards model will be used to compare the safety outcome between users of different OACs, weighted on the estimated PS according to the IPTW approach.
 - Proportionality assumption will be tested by use of Schoenfeld residuals.

Subgroup Analysis

- The potential heterogeneity of treatment effects in selected subgroups of patients with VTE will be examined for the major bleeding as follows:
 - Aged <65 years vs. aged \geq 65 years
 - Females vs. males
 - Setting of VTE diagnosis (inpatient vs. outpatient)
 - Type of VTE (DVT without PE [ICD-10: I80.2, I80.3] vs. PE with or without DVT [I26.0, I26.9])
 - Major orthopedic surgery-provoked VTE
 - Major orthopedic surgery-provoked VTE is defined as an event preceded by knee arthroplasty, hip arthroplasty, or hip fracture surgery (National Procedure Codes: N0305, N0601, N0611, N0641, N0711, N2070, N0715, N2710, N0731, N0981, N0991, N1711, N3710, N1721, N3720, N1715, N4710, N1725, N4720, N2072, N2077, N2712, N2717, N3712, N3717, N3722, N3727, N4712, N4717, N4722 or N4727) within 3 months period prior to index date
 - With vs. without CKD stage 3 or 4 (N18.3, N18.4)
- P-for-interaction value <0.05 will be used to denote a significant difference between the two groups.

Sensitivity Analysis

- Vary the definition of treatment interruption/discontinuation to 15 and 60 days (allowing for varying non-adherence) to assess the effect this had on study outcomes.
- Four other approaches involving PS will be applied to determine the robustness of our study findings. First, we will vary the extreme value of PS in trimming process (most extreme 5%, and 10% will be excluded). Second, we will include the estimated PS, in addition to other covariates, into our multivariable Cox proportional hazards regression model. Third, we will stratify on the estimated PS in deciles. Last, we will apply another weighting approach, standardized mortality ratio weights, with the weights given as follows: 1 for the treatment group of interest and PS/(1 – PS) for the comparator group.[4]

- Exclude patients with a history of bleeding during the 6-month pre-index-date period in Phase II comparative analysis to evaluate the robustness of findings with respect to changes in underlying risk of patients

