Table 17. Risk of major bleeding events in patients with venous thromboembolism who newly initiated oral anticoagulants associated with NOAC use versus warfarin	58
Table 18. Risk of major bleeding events by site, intracranial, gastrointestinal, all others, associated with NOAC use versus warfarin.....	59
Table 19. Subgroup analyses for the risk of major bleeding events associated with NOAC use versus warfarin.....	60
Table 20. Sensitivity analyses for the risk of major bleeding events associated with NOAC use versus warfarin.....	62

Table 1. Baseline characteristics among venous thromboembolism patients without active cancer by their index anticoagulant treatment

Characteristics	Warfarin-based therapy N= (%)	NOAC-based therapy N= (%)	PAC only N= (%)	p-value
Follow-up (days; median, IQR)				
Age (years; mean±std)				
Age group (years; n, %)				
18-40				
40-65				
≥65				
Sex (n, %)				
Male				
Female				
Index VTE event (n, %)				
DVT only				
PE with or without DVT				
Major orthopedic surgery-provoked VTE (n, %)				
Health insurance type (n, %)				
National health insurance				
Medical aid				
Veterans				
Index year (n, %)				
2013				
2014				
2015				
2016				
2017				
2018				
2019				
CCI score (mean±std)				
HAS-BLED score (mean±std)				
Comorbidities (n, %)				
Antiphospholipid syndrome				
Asthma				
History of cancer				
COPD				
Chronic kidney disease				
Chronic liver disease				
Diabetes mellitus				
Fracture				
Heart failure				
Hyperlipidemia				

PFIZER CONFIDENTIAL

Hypertension

Ischemic heart disease

Myocardial infarction

Stroke

Trauma

Previous use of medications

(n, %)

Corticosteroids

NSAIDs

ACE inhibitors

Angiotensin II receptor

blockers

Antiplatelets

β-blockers

Calcium-channel blockers

SSRI

Proton pump inhibitors

Diuretics

Thiazides

Vasodilators

Estrogens

Cyclooxygenase-2

inhibitors

Triazole antifungal agents

Outpatient visits (mean±std)

Note: ACE, angiotensin-converting enzyme; CCI, Charlson comorbidity index; COPD, chronic obstructive pulmonary disease; IQR, interquartile range; NOAC, non-vitamin K antagonist oral anticoagulant; NSAIDs, nonsteroidal anti-inflammatory drugs; PAC, parenteral anticoagulants; SSRI, selective serotonin reuptake inhibitors; std, standard deviation.

Table 2. Baseline characteristics among venous thromboembolism patients with active cancer by their index anticoagulant treatment

Characteristics	Warfarin-based	NOAC-based	PAC only	p-value
	therapy	therapy		
	N=	N=	N=	

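### The 3-month look-back for surgery-provoked VTE is counted from the anticoagulant start, not from the VTE, so the period covered before the VTE varies from 90 down to 60 days with treatment delay

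*SAP*

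**What the plan says.** Among the Phase II subgroups for major bleeding, SAP section 10 gives this definition: "Major orthopedic surgery-provoked VTE is defined as an event preceded by knee arthroplasty, hip arthroplasty, or hip fracture surgery". After a list of procedure codes it adds the time limit "within 3 months period prior to index date". Protocol 9.7 has the same definition and limit.

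SAP 8.2 (and Protocol 9.1) keeps two dates apart. For the VTE: "The cohort entry will be defined as the date of incident VTE diagnosis". For treatment: "The index date will be defined as the date of first prescription for anticoagulants within 30 days after the index VTE event". The two can therefore differ by 0 to 30 days.

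The flag is used in two places. It is a baseline row in SAP Table 1 (patients without active cancer), and in SAP Table 19 it defines a subgroup under the VTE etiology heading, with a hazard ratio and an interaction test. No separate definition is given for either table.

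**The concern.** The flag describes the cause of the VTE, so the interval that matters runs from surgery to VTE. The plan measures surgery to first anticoagulant. Two patients with the same operation and the same surgery-to-VTE interval can be classified differently only because one started treatment later.

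The sentence also has two reference points. The surgery must precede the event, but the window is counted from the index date. Two programmers could build different subgroups from it, depending on whether they code both conditions or only the window.

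At stake are who belongs to one Phase II subgroup and one descriptive frequency in Phase I.

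**Working it through.** **Inputs.**
- W, the window length: 3 months (SAP 10, Protocol 9.7). The documents do not convert this to days. I take W = 90 and check W = 92.
- L, days from VTE diagnosis to first anticoagulant: 0 to 30 (SAP 8.2). No distribution is given.

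The plan states no figure for this variable, so there is none to reproduce. The check is date arithmetic.

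**Formulas.** Put the VTE at day 0, so the index date is day L. The window runs from day L - W to day L.
- Look-back before the VTE = W - L days.
- Operations missed = those from W - L + 1 to W days before the VTE. With W = 90 this is 91 - L to 90.
- Post-VTE days inside the window = L. These matter only if the requirement that surgery precede the event is not coded.

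**Results, W = 90.**

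| L | Window relative to VTE | Look-back before VTE | Operations missed (days before VTE) | Post-VTE days in window | Share of window |
|---|---|---|---|---|---|
| 0 | -90 to 0 | 90 | none | 0 | 0% |
| 7 | -83 to +7 | 83 | 84 to 90 | 7 | 7/90 = 7.8% |
| 14 | -76 to +14 | 76 | 77 to 90 | 14 | 14/90 = 15.6% |
| 30 | -60 to +30 | 60 | 61 to 90 | 30 | 30/90 = 33.3% |

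With W = 92 and L = 30 the window is -62 to +30, the look-back is 62 days and the post-VTE share is 30/92 = 32.6%. The choice of 90 or 92 makes little difference.

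**Missed case.** Knee arthroplasty 80 days before the VTE, first anticoagulant 14 days after it. Surgery is 80 + 14 = 94 days before the index date, outside the window for W = 90 or 92. The same patient treated on the day of the VTE has surgery 80 days before the index date and is inside. This follows whether or not the precedence requirement is coded.

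**Post-VTE case.** DVT on day 0, hip surgery on day 3, first anticoagulant on day 5. Surgery is 5 - 3 = 2 days before the index date, so it falls in the window. It did not precede the DVT, however, so the full sentence excludes it. The patient enters only if the window alone is programmed.

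**Does other text settle the anchor?** SAP 8.2 sets baseline clinical characteristics to the period before the index date unless SAP 8.4 says otherwise, and 8.4 says nothing about this variable. The plan does use the VTE as an anchor elsewhere: prior VTE is assessed "within the 12-month period prior to the index VTE encounter", and exclusion 4 on prior anticoagulation uses the same reference point. The VTE date is thus already derived.

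**The case against.** The strongest reply is that the sentence already requires the event to be preceded by surgery. A reader might infer from the window that operations after the VTE will be counted as its cause. Read literally, the definition excludes them, and the last two columns of the table apply only if half of it is ignored. This stands. What remains on that side is a risk of inconsistent programming.

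Second, a reader might infer that the subgroup hazard ratio is biased. The documents do not show this. The estimate is a weighted comparison of each NOAC with warfarin within the subgroup. Reclassifying patients changes whom it describes, but distorts the ratio only if the drug effect differs between rightly and wrongly classified patients, or if the errors bring in confounding that the weights miss. Neither can be shown from the plan. This also stands.

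Third, it is tempting to say that the misclassified patients are those whose anticoagulant was delayed by the operation. Nothing in the documents supports that. The index drug may be any anticoagulant, including heparin, and SAP 8.4 notes that heparin can be started in the acute stage. In the post-VTE example, heparin given at diagnosis would put the index date before the surgery.

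Fourth, the index date is the usual anchor in this plan: comorbidities, medications, scores and exclusions 2, 3, 6 and 7 all use it. That explains how the wording arose. It does not justify it here, because this flag is presented as VTE etiology and not as patient status at treatment start.

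None of these replies touches the shortened look-back.

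**Conclusion.** The point holds as a defect in the definition of one flag. As written, the look-back before the VTE is 90 - L days, from 90 for same-day starters to 60 at the longest permitted lag. Operations 91 - L to 90 days before the VTE are missed whenever L is above 0. This rests on 3 months being 90 days; with 92 days the range is 92 to 62.

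Admission of post-VTE operations, up to L days and at most 30, is conditional on the precedence requirement being left out of the program. It should not be stated as what the plan does.

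The consequence is limited. One Phase II subgroup is affected, in a phase that is itself conditional on sufficient power, along with one row of SAP Table 1. Patients treated on the day of diagnosis are classified correctly. The flag is not among the listed confounders in SAP 8.4 or the rows of Tables 13 to 16, so the primary comparison is unaffected. Without the distribution of L, the number misclassified and the size and direction of any effect on the subgroup hazard ratio remain unknown. This is a minor correction, worth making before programming.

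**What to change.** In SAP section 10 and Protocol 9.7, replace "within 3 months period prior to index date" with: *within 3 months before the index VTE diagnosis date (cohort entry), with the surgery date before the VTE date*. State in SAP Tables 1 and 19 that both use this flag.

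Every patient then has the same look-back whatever the treatment delay, and post-VTE operations are excluded explicitly. Surgery on the day of diagnosis does not qualify under this wording; the study team should confirm that this is intended.

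The cost is one phrase in each document and one changed anchor in the code. No new data are needed, because the cohort-entry date is already derived. Tabulating the VTE-to-index lag would show how many patients could be affected.

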- In the NOAC-based group, all analyses will be repeated stratified by each individual NOAC class (e.g, apixaban, dabigatran, rivaroxaban, edoxaban) to

PFIZER CONFIDENTIAL

identify the difference in baseline characteristics and treatment patterns between each NOAC class.

- To identify potential reasons for treatment change, clinical events preceding the first treatment change (major bleeding, thromboembolism diagnosis, complications of VTE, major surgery, active cancer, a new diagnosis of CKD or AKI, a new diagnosis of liver disease or abnormal liver function) will be measured within 30 days prior to the first date of treatment change. Patients can contribute with multiple events.
- All analyses of treatment patterns will be presented stratified according to the index anticoagulant treatment, and not overall or per drug class.

Phase II of the study (comparative)

Propensity score analysis

- To balance and adjust for any potential differences in baseline sociodemographic and clinical characteristics between treatment groups, propensity score (PS) methods will be implemented.
 - A logistic regression model will be used to estimate the predicted probability (propensity) of initiating each NOAC compared with warfarin given baseline covariates mentioned above. By using the estimated PS, we will apply the PS based on the inverse probability of treatment weights (IPTW), where the treatment group of interest will be given a weight of 1/PS, and the comparator group will be given a weight of 1/(1-PS) [4, 5]. The most extreme 1% of PS values (IPTW with trimming) will be excluded to improve comparability between exposure groups.

Main Analysis

- Sociodemographic and clinical characteristics will be summarized with means (STD) or median (IQR) for continuous variables and with count (proportions) for categorical variables for the two treatment comparisons of: apixaban vs warfarin, rivaroxaban vs warfarin, edoxaban vs warfarin and dabigatran vs warfarin (and NOAC vs NOAC, if scientifically feasible).
 - Differences in baseline covariates between users of different OACs will be assessed using the SD where the absolute SD <0.1 will be considered as well balanced.
- The incidence rate of major bleeding overall and by site will be presented as the total number of events per 1,000 person-years, with its 95% CIs estimated using the Poisson distribution.

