Table 18. Risk of major bleeding events by site, intracranial, gastrointestinal, all others, associated with NOAC use versus warfarin

	No of Patients	No of Events	Person-years	Incidence rate* (95% CI)	Crude HR (95% CI)	IPT-Weighted HR (95% CI)
Intracranial bleeding						
Warfarin-based						Reference (1.00)
Apixaban						
Rivaroxaban						
Edoxaban						
Dabigatran						
Gastrointestinal bleeding						
Warfarin-based						Reference (1.00)
Apixaban						
Rivaroxaban						
Edoxaban						
Dabigatran						
All other sites						
Warfarin-based						Reference (1.00)
Apixaban						
Rivaroxaban						
Edoxaban						
Dabigatran						

Note: CI, confidence interval; HR, hazard ratio; IPT, inverse probability of treatment.

*Events per 1000 person years.

Table 19. Subgroup analyses for the risk of major bleeding events associated with NOAC use versus warfarin

	No. of Patients	No. of Events	IPT-Weighted HR (95% CI)	P _{interaction} *
Age				
<65 years				
Warfarin-based			Reference (1.00)	
Apixaban				
Rivaroxaban				
Edoxaban				
Dabigatran				
≥65 years				
Warfarin-based			Reference (1.00)	
Apixaban				
Rivaroxaban				
Edoxaban				
Dabigatran				
Sex				
Female				
Warfarin-based			Reference (1.00)	
Apixaban				
Rivaroxaban				
Edoxaban				
Dabigatran				
Male				
Warfarin-based			Reference (1.00)	
Apixaban				
Rivaroxaban				
Edoxaban				
Dabigatran				
VTE diagnosis setting				
Inpatient				
Warfarin-based			Reference (1.00)	
Apixaban				
Rivaroxaban				
Edoxaban				
Dabigatran				
Outpatient				
Warfarin-based			Reference (1.00)	
Apixaban				
Rivaroxaban				
Edoxaban				
Dabigatran				
Type of VTE				
DVT without PE				
Warfarin-based			Reference (1.00)	

Apixaban

Rivaroxaban

Edoxaban

Dabigatran

PE with or without DVT

Warfarin-based

Reference (1.00)

Apixaban

Rivaroxaban

Edoxaban

Dabigatran

VTE etiology

Major orthopedic

surgery-provoked VTE

Warfarin-based

Reference (1.00)

Apixaban

Rivaroxaban

Edoxaban

Dabigatran

Chronic kidney disease

With CKD stage 3 or 4

Warfarin-based

Reference (1.00)

Apixaban

Rivaroxaban

Edoxaban

Dabigatran

Without CKD stage 3 or 4

Warfarin-based

Reference (1.00)

Apixaban

Rivaroxaban

Edoxaban

Dabigatran

Note: CI, confidence interval; DVT, deep vein thrombosis; HR, hazard ratio; IPT, inverse probability of treatment; PE, pulmonaryembolism; VTE, venous thromboembolism

*P for interaction will be calculated between warfarin-based therapy and each NOAC.

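### Any of 20 subgroup interaction tests with p below 0.05 counts as a significant difference, with no multiplicity control or exploratory label; weighted subgroup HRs have no planned within-subgroup balance check, and one factor lacks a comparison level

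*SAP*

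**What the plan says.** SAP section 10 (Phase II, Subgroup Analysis) introduces the subgroups with "The potential heterogeneity of treatment effects in selected subgroups of patients with VTE will be examined for the major bleeding as follows". It lists age, sex, setting of diagnosis, type of VTE, orthopaedic surgery-provoked VTE and CKD stage 3 or 4. Five of these are written as two-level contrasts, for example "Setting of VTE diagnosis (inpatient vs. outpatient". The orthopaedic item has only a definition: "Major orthopedic surgery-provoked VTE is defined as an event preceded by knee arthroplasty, hip arthroplasty, or hip fracture surgery". The list is followed by the decision rule: "P-for-interaction value <0.05 will be used to denote a significant difference between the two groups". Protocol section 9.7 has the same list and rule.

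The footnote to SAP Table 19 adds: "P for interaction will be calculated between warfarin-based therapy and each NOAC". The comparisons are "apixaban vs warfarin, rivaroxaban vs warfarin, edoxaban vs warfarin and dabigatran vs warfarin (and NOAC vs NOAC, if scientifically feasible"; Table 19 has rows for the four NOAC-warfarin comparisons only.

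On weighting, the SAP says: "A logistic regression model will be used to estimate the predicted probability (propensity) of initiating each NOAC compared with warfarin". Balance means an absolute standardized difference (SD) below 0.1, and it is displayed in Tables 13 to 16, one per comparison, for the whole cohort. Table 19 reports IPT-weighted HRs within each subgroup level. The SAP does not say how the weights for those HRs are obtained.

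**The concern.** There are two separate problems and one omission.

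First, the rule turns each p-value into a claim. With 20 or more tests at 0.05 each, a claimed difference in some NOAC's bleeding effect by age, sex, setting, VTE type or kidney disease is likely to arise by chance, and the plan gives the reader no warning of this.

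Second, weights that balance a whole cohort need not balance each subgroup if drug choice depends on covariates differently in the two levels. The interaction then partly measures differential confounding. The risk is concrete here:
- Diagnosis setting and orthopaedic surgery-provoked VTE are subgroup factors but are not in the SAP 8.4 list of potential confounders.
- The CKD covariate is N18 and N19, while the subgroup is N18.3 and N18.4.
- VTE type is a listed confounder and a subgroup factor, but has no row in Tables 13 to 16.

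Third, the orthopaedic factor has no complement in the text or in Table 19, so its interaction p-value has no defined contrast.

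**Working it through.** The documents state no family-wise error, number of interaction tests or power for interaction, so there is no figure of theirs to reproduce. The study-size sections address main effects only.

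**Number of tests.** Five two-level factors × 4 comparisons = 20 as written. With an orthopaedic complement, 6 × 4 = 24.

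**Independent tests, no true interaction anywhere.** The chance of at least one p below 0.05 is 1 − 0.95^k.
- k = 20: 1 − 0.95^20 = 0.642; expected false claims 20 × 0.05 = 1.0.
- k = 24: 1 − 0.95^24 = 0.708; expected 24 × 0.05 = 1.2.

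**Shared warfarin group.** The four tests within a factor are correlated. With a common event rate, corr(i, j) = (1/W) / √[(1/Ni + 1/W)(1/Nj + 1/W)]. The inputs are the projected sizes in SAP section 9: warfarin W = 29,862, apixaban 19,362, rivaroxaban 61,593, edoxaban 13,300, dabigatran 6,062. The correlations are 0.23 to 0.51. The simulated chance of at least one false claim is:

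| Assumption | 20 tests | 24 tests |
|---|---|---|
| Independent | 64.2% | 70.8% |
| Shared warfarin group | 60.1% | 66.8% |
| Also correlation 0.3 between factors | 56.6% | 62.9% |
| Arm-specific event rates from SAP section 9 (1.19% to 8.5%), warfarin rate varied over 1.19% to 8.5% | 55–63% | 61–69% |

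The figure drops below 50% only if the tests within a factor correlate above about 0.7 (20 tests) or 0.8 (24 tests). With perfect correlation within each factor it is 1 − 0.95^5 = 22.6% or 1 − 0.95^6 = 26.5%.

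**Whole-cohort weights within subgroups.** The documents give no inputs, so these are assumptions: a binary covariate with 30% prevalence that triples the hazard, no drug effect, and a propensity model with main effects only. Let b be the covariate's log-odds effect on drug choice in a subgroup level, and b̄ the single value that the whole-cohort model fits. After weighting, the prevalence gap between arms in that level is about (b − b̄) × 0.3 × 0.7. The SD is about (b − b̄) × √0.21. The spurious HR is (1 + 2p1)/(1 + 2p0), where p1 and p0 are the weighted prevalences in the two arms.

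For b = −0.4 in 60% of patients and +0.4 in 40%, b̄ ≈ −0.08:
- First level: gap −0.32 × 0.21 = −0.067; SD −0.15; HR ≈ (1.6 − 0.067)/(1.6 + 0.067) = 0.92.
- Second level: gap 0.48 × 0.21 = 0.101; SD +0.22; HR ≈ (1.6 + 0.101)/(1.6 − 0.101) = 1.13.
- Ratio of HRs: about 1.23, with overall SD about 0.

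The range over milder inputs, by exact population calculation:

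| Effect on drug choice (split) | Within-level SDs | Ratio of HRs |
|---|---|---|
| −0.4 / +0.4 (60/40) | −0.15, +0.22 | 1.23 |
| −0.2 / +0.2 (60/40) | −0.07, +0.11 | 1.11 |
| −0.1 / +0.1 (60/40) | −0.04, +0.05 | 1.05 |
| +0.2 / +0.4 (50/50) | −0.05, +0.05 | 1.05 |

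Overall SD is about 0 in every row. Letting the covariate effect in the propensity model differ by level removes the imbalance and returns the ratio to 1.00.

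**The case against.** These are pre-specified subgroups, few in number and listed apart from the main analysis, in a phase that is itself conditional on power and feasibility. The stated purpose is to examine potential heterogeneity, and the Phase II objective is the overall comparison. That is a fair reason not to demand formal error control. It does not answer the decision rule, which names each p below 0.05 a significant difference and carries no exploratory label.

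A reader might infer that the plan carries whole-cohort weights into the subgroups. The documents do not say so; they are silent on whether the score is refitted. What can be said is that no method is stated and no balance check within subgroups is planned.

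The ratio of 1.23 needs a strong prognostic covariate whose effect on drug choice reverses sign between levels. With same-direction effects the ratio is about 1.05 and both SDs pass the plan's own limit. So the example shows what can happen, not what is expected.

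A strict remedy also has costs. Refitting a large propensity model in small strata, such as dabigatran users with CKD stage 3 or 4, can give unstable weights. With 100 patients per arm, an SD has a standard error of about √(2/100) = 0.14, so an HR withheld at 0.1 would often be withheld by chance.

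**Conclusion.** The point holds in three parts. The unadjusted rule gives about a 60% chance of at least one false claim over the 20 tests as written (55–64% across the assumptions shown), and about 67% over 24. The 24 count needs a comparison level that the plan does not define. These figures assume that no true interaction exists for any factor or drug, and that each test truly runs at 0.05; the SAP names no robust variance for the weighted Cox model. They describe the whole set of tests. A reader might take them as the chance that a particular reported interaction is false, but the documents give no basis for that.

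The missing subgroup weighting method and balance check is a separate bias concern. It adds nothing to the 60% figure, which comes from the test count alone. Its size is illustrative: a spurious HR ratio of 1.05 to 1.23.

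The missing orthopaedic comparison level is a plain omission. The main analysis is not affected by any of this, but what the study may claim about subgroups is.

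**What to change.** 1. In SAP section 10 and Protocol 9.7, replace the p-value rule with the interaction HR ratio and its 95% CI, labelled exploratory, and state how many interactions are examined. Holm adjustment is optional; if used, the smallest p would need to be below 0.05/20 = 0.0025, or 0.05/24 = 0.0021.
2. State how weights are obtained for Table 19 and report weighted SDs within each subgroup level. Where any is 0.1 or more, let the propensity score vary by that subgroup, through subgroup-by-covariate terms or a refit where numbers permit. Flag, rather than withhold, HRs that remain imbalanced.
3. Add patients without orthopaedic surgery-provoked VTE as the comparison level in the subgroup text of both documents and in Table 19.

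The cost is some extra programming, wording and table changes, fewer nominal interaction claims, and less stable weights in small strata. No new data are needed.
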